## 7 Data Management Procedures

All personal information is strictly confidential and no names will be disclosed except as required by law. All information and data collected during this research will be recorded in a spreadsheet. This spreadsheet will not contain protected health information. The spreadsheet will be stored in a secure password protected folder on a laptop that only the study Investigators will have access to and will be permanently deleted following publication of any and all manuscripts, if any, written as a result of this research. Records related to this study will be securely retained

Version 3.0 6/19/2019

#### A Randomized, Control Clinical Trial: The Effect of Different Injection Regimens of Autologous Conditioned Plasma for the Treatment of Symptomatic Knee Osteoarthritis [name]. Page 6 of 7

in a secure location for a period of 3 years after the completion of the study or longer as required by law. At that time, all records will be properly destroyed.

# 8 Data Analysis

All data will be entered into Surgical Outcomes System (SOS) & Research Electronic Capture Database (REDCap) and descriptive data will be compiled.

# 9 Statistical Considerations

A power analysis was performed to determine sample size based upon recent clinical trials comparing PRP to HA for the treatment of osteoarthritis. Analysis utilized the average of standard deviation to detect average of group mean effect at 80% power. This determined that 25 patients per group would be needed to reach statistical significance with the WOMAC.

Ranges, means and standard deviations for all measures will be determined and calculated. Data will be analyzed for differences between groups using a repeated measures ANOVA design, using a significant p-value of < 0.05 for rejecting the null hypothesis.

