## 1 Background / Scientific Rationale

In the United States it is estimated that 47 million people have been diagnosed with arthritis. 4.3 million have been diagnosed with isolated osteoarthritis of the knee and knee arthritis accounts for 20% of disability claims [1]. Prevalence of the disease continues to climb and is expected to double by 2030. In addition, 4 out of 5 patients with osteoarthritis have movement limitations [1]. Currently there are no curative treatments for osteoarthritis. Surgical options include arthroscopy, osteotomies, and total joint replacement, but not all patients with knee osteoarthritis are candidates for surgical treatments, and others choose non-operative treatments instead of undergoing a procedure. Non-surgical treatment options include medications such as non-steroidal anti-inflammatory's (NSAIDs), injectables such as corticosteroids and hyaluronic acid, or physical treatments such as rehabilitative therapy, unloading braces, and activity modifications (i.e. canes or walkers). Additionally, weight loss can help in the battle to reduce pain in cases of knee osteoarthritis.

The clinical efficacy of hyaluronic acid or corticosteroid injections has been reported, but effects are short lived. This has led to the development of additional injection options such as autologous derived blood products which have been documented to alleviate symptoms related to knee osteoarthritis, with recent comparative studies suggesting a greater, long-lasting effect with these blood derived products like platelet rich plasma (PRP) [2-8]. One clinically-developed preparation of platelet rich plasma, named autologous conditioned plasma (ACP), has randomized controlled trial data proving efficacy [4,9]. Clinical use of platelet rich plasma for knee arthritis typically involves a 3-injection series over 3 weeks, i.e. an injection once a week for three weeks. Currently, all three orthopedic providers in this study use ACP to treat patients with knee osteoarthritis in common accepted clinical practice.

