# 2 **Objectives**

The main objective of this study is to determine if hyaluronic acid (HA) injected at the same time as autologous conditioned plasma (ACP), a leukocyte-poor platelet rich plasma product, will improve the performance of ACP in the treatment of symptomatic knee osteoarthritis. We hypothesize that the injection of hyaluronic acid will improve the efficacy of ACP.

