# 4 Participant Enrollment

80 patients will be recruited through the Andrews Institute physician practices. Potential participants will be prescreened for inclusion and exclusion criteria through standard of care medical evaluations. Once a potential participant has agreed to be involved in the study, they will go through the described informed consent process. Patients meeting the inclusion criteria will have the study explained to them by one of the members of the investigating team, and they will be given an opportunity to participate if they are interested. No specific advertising or recruitment material will be utilized.

Participant will also be instructed that they must not take any prescription or over the counter non-steroidal anti-inflammatory drugs (NSAIDS) for 1 week prior to the first injection until after the final injection. The participants will then be randomly placed in one of the two study groups and be scheduled to receive a three-injection series of autologous conditioned plasma injection or a two-injection series of autologous conditioned plasma and hyaluronic acid and a third injection on the third week of ACP in their involved knee. For The group receiving autologous conditioned plasma and hyaluronic acid, HA will be an additional injection on the first two injections and the third injection will be ACP alone. This regimen was selected to reflect the current evidence-based regimens for ACP and HA independently.

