## 5 Study Design and Procedures

Study design will be randomized control trial. Participants who meet the inclusion criteria will have the study explained in detail and informed consent will be obtained as outlined above. Participants will complete patient reported outcome questionnaires prior to their injection. The questionnaires will include the Western Ontario and McMaster University's Osteoarthritis Index (WOMAC), International Knee Documentation Committee Subjective Knee Evaluation Form (IKDC), Knee Injury and Osteoarthritis Outcome Score (KOOS). The WOMAC is 24 questions and takes approximately 2-5 minutes, the IKDC is 19 questions and takes 3-5 minutes, and the KOOS is 42 items and takes approximately 5-10 minutes. Participants will also complete these questionnaires at 1, 3, 6, 12, 18, and 24 months after the final injection.

Version 3.0 6/19/2019

#### A Randomized, Control Clinical Trial: The Effect of Different Injection Regimens of Autologous Conditioned Plasma for the Treatment of Symptomatic Knee Osteoarthritis [name]. Page 5 of 7

A trained medical professional will draw blood from the patients arm and the blood will be spun in a centrifuge for 5 minutes at 1500 RPM. The platelets will then be separated off for injection into the patient's knee. The treating physician will then inject the ACP into the involved knee joint following standard aseptic technique per the physician's standard of care. This entire process will be completed in a single patient visit. Any unused portion of a sample in the physician's office will be disposed of through standard biohazard waste disposal systems as required by law.

Group 1 [ACP]: Will receive 3 intra-articular injections of autologous conditioned plasma dosed at once a week for 3 weeks. Group 2 [ACP-HA]: Will receive 2 intra-articular injections of autologous conditioned plasma and hyaluronic acid once a week for 2 weeks and a third injection on the third week of ACP.

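### The plan's only test is an unspecified repeated measures ANOVA; a baseline-adjusted mixed model on all available scores would close the gaps at almost no cost, with a precision gain from about nil to large

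*Combined protocol and SAP*

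**What the plan says.** Section 9 (Statistical Considerations) has a single inferential sentence: "Data will be analyzed for differences between groups using a repeated measures ANOVA design". The threshold that it sets is p < 0.05. Otherwise Sections 8 and 9 cover only data entry, descriptive statistics and a sample size statement that "25 patients per group would be needed to reach statistical significance with the WOMAC". Section 4 states that "80 patients will be recruited".

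Section 5 schedules the scores. "Participants will complete patient reported outcome questionnaires prior to their injection", and "Participants will also complete these questionnaires at 1, 3, 6, 12, 18, and 24 months after the final injection". That gives seven scores per participant on each of WOMAC, IKDC and KOOS.

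The objective in Section 2 is directional: whether adding HA "will improve the performance of ACP in the treatment of symptomatic knee osteoarthritis".

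No section says whether baseline is a covariate, a level of time or subtracted. None says whether the test is a group main effect, a group-by-time interaction or a visit contrast, or what happens when a questionnaire is missed.

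**The concern.** With seven scores, the sentence in Section 9 can mean several different tests. Three are single-degree-of-freedom group comparisons: (a) the group main effect over all seven scores, (b) the group effect over the follow-up scores only, and (c) change from baseline. A fourth is the group-by-time interaction on 6 degrees of freedom, which does not say which arm is better. Reading (a) also averages in a score taken before treatment, which shrinks a constant effect to 6/7 of its size.

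Two things are at stake. With one significance threshold and no named contrast, the choice among these tests can be made after the data are seen. And each of (a) to (c) fixes the weight on baseline in advance, so the best of them depends on a correlation that the documents do not give. If incomplete records were also dropped, a participant who answered most of the questionnaires would add nothing to the comparison.

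**Working it through.** **Inputs from the documents.** 80 patients in two groups (Section 4); one baseline and six follow-ups (Section 5); p < 0.05, 80% power and 25 per group on WOMAC (Section 9).

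**Assumptions, not in the documents.** 1:1 allocation (40 per group), two-sided testing, effect d in SD units, correlation r between scores, and all response patterns.

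**1. The plan's own figure.** 25 per group cannot be reproduced, because no difference or SD is given. Solved backwards, d = (1.960 + 0.842) × √(2/25) = 0.79 by the normal formula, or 0.81 by the two-sample t-test.

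**2. Why adjustment is not less precise.** Let Y be the follow-up contrast (weights sum to 1), b the baseline in SD units and c = cov(Y, b). Scaled to estimate the same effect, each single-contrast reading tests Y + k·b:

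- (a), with Y the six-visit mean: (6Y + b)/7 × 7/6 = Y + b/6, so k = +1/6
- (b): k = 0
- (c): k = −1

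The variance is var(Y) + 2kc + k². The baseline-adjusted variance is var(Y) − c². The difference is (k + c)², which is never negative, and equal correlation is not needed. Estimating the covariate multiplies the adjusted variance by about 1 + 1/76 = 1.013.

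Check for the six-visit mean at r = 0.5: var(Y) = (1 + 5 × 0.5)/6 = 0.583 and the adjusted variance is 0.583 − 0.25 = 0.333. Then (a) is 0.333 + 0.667² = 0.778, (b) is 0.333 + 0.5² = 0.583 and (c) is 0.333 + 0.5² = 0.583. The ratios to adjusted are 2.33, 1.75 and 1.75.

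**3. Power with complete data.** Noncentral t, noncentrality d/√(2V/40), 78 df (77 adjusted). At d = 0.5 and r = 0.5 the noncentrality is 0.5/√(0.333/20) = 3.87 adjusted and 0.5/√(0.583/20) = 2.93 for (b).

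| Contrast, constant effect | r | (a) | (b) | (c) | Adjusted |
|---|---|---|---|---|---|
| Six-visit mean, d = 0.5 | 0.3 | 85% | 93% | 69% | 97% |
| | 0.5 | 71% | 82% | 82% | 97% |
| | 0.7 | 59% | 72% | 96% | 99% |
| One named visit, d = 0.5 | 0.3 | – | 60% | 46% | 64% |
| | 0.5 | – | 60% | 60% | 72% |
| | 0.7 | – | 60% | 81% | 87% |

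The order of (b) and (c) reverses between r = 0.3 and r = 0.7; the adjusted analysis is at or above both.

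**4. Where the gain is small.**

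- At d = 0.81, six-visit mean, complete data: every single-contrast reading has 94% or more, so the gain is 0 to 6 points.
- Baseline correlation 0.3, follow-ups correlated 0.6, six-visit mean at d = 0.5: (a) 70%, (b) 77%, (c) 57%, adjusted 83%.
- The 24-month visit alone, with correlation 0.6 to 0.8 per visit step: the correlation with baseline is 0.6⁶ = 0.05 to 0.8⁶ = 0.26. At d = 0.5, adjusted power is 59–62% against 60% for (b).

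**5. Missing questionnaires, relevant only if incomplete records are dropped.** Six-visit mean, d = 0.5, r = 0.3/0.5/0.7:

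- Independent 90% response per visit leaves 0.90⁶ = 53%, about 21 of 40. Simulated complete-case power is 67/56/45% for (b) and 43/54/75% for (c). The mixed model on the same data has 97/98/99%.
- The same average response as monotone dropout, from 100% to 80%, leaves 32 of 40. Complete-case power is 86/73/62% for (b) and 59/73/91% for (c). The mixed model has about 96/96/99%, and most of that gap comes from baseline adjustment rather than recovered records.

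The simulations used an unstructured covariance and residual degrees of freedom, not Kenward-Roger. There were 600–700 runs per power figure (standard error about 2 points or less). Type I error was 4.7% in 1,500 null runs at r = 0.5 with 90% response.

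**6. A fading effect.** Section 1 says of existing injections: "The clinical efficacy of hyaluronic acid or corticosteroid injections has been reported, but effects are short lived". Suppose d = 0.5 at 1, 3 and 6 months and zero afterwards, with complete data. The six-visit mean effect is then 0.25. Adjusted power for that mean is 49/48/58%, against 74/89/99% for the 6-df interaction. For the mean of 1, 3 and 6 months, adjusted power is 91/93/98%. Here the choice of contrast matters more than the adjustment.

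**The case against.** The strongest reply is that the plan never states the method being criticised. Section 9 does not say that baseline is a level of time or that incomplete records are dropped. If the intended ANOVA has baseline as a covariate and data are complete, the two analyses essentially coincide. This stands: the documents show under-specification, not a demonstrably poor method. A reader might infer that the plan discards incomplete records or analyses baseline as an outcome; the text supports neither.

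Second, at the effect implied by the sample size, 80 patients already give ample power on complete data. This also stands for the six-visit mean. It is limited by the source of that effect: Section 9 sizes the trial on studies of PRP against HA, whereas this trial adds HA to ACP. Nothing in the documents shows that the add-on effect is as large.

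Third, the interaction test can be more powerful when the effect fades. True, but it answers whether the profiles differ in shape, not the directional question in Section 2, and it gives no single between-arm estimate.

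Fourth, independent loss at each visit is an unfavourable pattern for complete-case analysis. That is right, so the monotone case is shown beside it.

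**Conclusion.** The point holds as a matter of specification, with a precision benefit of uncertain size. Section 9 should state how baseline enters, which contrast is tested and how missing scores are handled. A baseline-adjusted mixed model does this and, for the same follow-up contrast, is never less precise than readings (a) to (c) beyond about 1% in variance.

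The gain runs from about nil (a late visit with decaying correlation compared with follow-up-only, or an ANOVA that already adjusts with complete data), through 0 to 6 points (d = 0.81, six-visit mean, complete data), to larger differences at d = 0.5. All of this rests on assumed correlations, effects, allocation and response patterns.

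Three stronger readings are not supported. Repeated measures ANOVA is not invalid in itself. The trial is not shown to be underpowered. And the contrast between 97–99% and 45–67% is not the expected benefit: it needs d = 0.5, dropped records and independent loss at every visit.

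**What to change.** Replace the inferential sentence in Section 9 with wording such as:

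> WOMAC will be analysed in all randomised participants with at least one follow-up score, in the group assigned, by a linear mixed model for repeated measures on all available follow-up scores. Fixed effects are arm, visit, arm-by-visit, baseline score and baseline-by-visit. The covariance is unstructured, with [named structure] as fallback if the model does not converge, and Kenward-Roger degrees of freedom are used. The primary comparison is ACP-HA minus ACP at [named visit, or mean over named visits], with a 95% confidence interval. Other visits, and IKDC and KOOS under the same model, are secondary. A delta-adjusted sensitivity analysis will examine departures from missing at random.

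The sponsor must fill both brackets before any outcome data are examined; left blank, the text would repeat the present omission. WOMAC is used because Section 9 sizes the trial on it. The six-visit mean suits a sustained effect but loses power if the effect fades, so the contrast should follow from when benefit is expected.

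The cost is analysis wording only. All the scores are already scheduled. Adjustment uses one degree of freedom and about 1% in variance if baseline proves uninformative.

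### Section 9 does not declare which instrument or which ANOVA term decides the single hypothesis, so the 5% error rate is not guaranteed

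*Combined protocol and SAP*

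**What the plan says.** Section 2 poses one directional question: "We hypothesize that the injection of hyaluronic acid will improve the efficacy of ACP". It is not tied to an instrument or a time.

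Section 5 lists three questionnaires (WOMAC, IKDC, KOOS). On timing it says "Participants will complete patient reported outcome questionnaires prior to their injection" and "Participants will also complete these questionnaires at 1, 3, 6, 12, 18, and 24 months after the final injection". Counting one pre-injection completion, that is seven occasions per instrument.

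Section 9 gives the sample size basis: "Analysis utilized the average of standard deviation to detect average of group mean effect at 80% power", with the result that "25 patients per group would be needed to reach statistical significance with the WOMAC". It then says "Ranges, means and standard deviations for all measures will be determined and calculated", followed directly by the only inferential sentence in the plan: "Data will be analyzed for differences between groups using a repeated measures ANOVA design, using a significant p-value of < 0.05".

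Section 8 adds only data entry and descriptive summaries. No section names a primary outcome, a particular WOMAC score, the deciding ANOVA term, a primary visit, the role of the pre-injection score, or a rule for several tests.

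**The concern.** A repeated measures ANOVA of one instrument gives at least two results that could be read as an effect of HA: the group term (a difference in level averaged over occasions) and the group-by-time term (a difference in course). Three instruments make six such results. The plan has one hypothesis and one threshold, and does not say which result the threshold applies to.

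Two things are at stake:

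- **Error rate.** If the deciding result is picked after the data are seen, the chance of a false claim exceeds 5%. The answer for a treatment that works may also depend on the pick.
- **Power, a separate matter.** A score taken before treatment cannot reflect treatment. If it enters as a seventh level of time, it dilutes the group term. As a covariate, the same score would sharpen the comparison.

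**Working it through.** **Inputs from the documents:** threshold 0.05; three instruments; six follow-up visits plus one pre-injection score (Section 5); 25 per group at 80% power (Section 9); 80 patients to be recruited (Section 4).

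**Assumed:** equal split, so 40 per group; two-sided tests; no dropout; equal correlation p between any two occasions (0.6 unless stated); correlation r between instruments.

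**1. The plan's own figure.** The 25 per group cannot be reproduced, because no mean difference or SD is given. Solving backwards, d = (1.960 + 0.842) × √(2/25) = 0.79 SD by the normal formula, and 0.81 SD by the t-test.

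**2. WOMAC only, either term may decide.** Under equal correlation the two tests are practically independent: 1 − 0.95² = 9.75%. A null simulation (40 per group, seven occasions, 20,000 trials per setting) gave 9.5% to 10.0%, with each single test at 4.7% to 5.3%. Counting only errors that favour HA, the figure is about 5% against a nominal 2.5%.

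**3. One term, any of three instruments may decide.** If independent, 1 − 0.95³ = 14.3%. With equal correlation r, by numerical integration of a trivariate normal:

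| r | 0.5 | 0.7 | 0.8 | 0.9 | 0.95 |
|---|---|---|---|---|---|
| Two-sided error | 12.5% | 10.9% | 9.8% | 8.4% | 7.3% |
| Favouring HA (nominal 2.5%) | 6.3% | 5.5% | 4.9% | 4.2% | 3.7% |

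**4. Either term, any instrument.** At r = 0, 1 − 0.95⁶ = 26.5%. Simulation gave 26.5% at r = 0 and 16.5% at r = 0.9.

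**5. Do the two WOMAC terms agree when HA works?** Take a constant follow-up difference d (in SDs), zero before injection, n per group, p = 0.6.

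- Group term with seven levels: signal-to-noise per unit d is (6/7)/√((1+6p)/7) = 0.857/0.811 = 1.06. The 6/7 is the dilution from the pre-injection level. At d = 0.5 and n = 40 the power is 64.6%.
- Group-by-time: noncentrality (n/2)(6/7)d²/(1−p) = 20 × 0.857 × 0.25/0.4 = 10.71 on 6 and 468 degrees of freedom. The power is 67.3%.
- Disagreement: 0.646 × 0.327 + 0.354 × 0.673 = 44.9% (45.5% simulated).

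Across p = 0.4 to 0.8 disagreement is 44% to 52% at d = 0.5. At d = 0.81 it is 4% to 9% with 40 per group, and 22% to 32% with 25.

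**6. Power of the candidate tests** (40 per group, p = 0.6). With the pre-injection score as covariate, signal-to-noise per unit d is 1/√((1+5p)/6 − p²) = 1/√0.307 = 1.81 for the six-visit average, and 1/√(1−p²) = 1.25 for one visit. The fading profile is illustrative: 0.5 SD at months 1 and 3, 0.25 at month 6, then 0. Its mean is 1.25/6 = 0.208 over six visits and 1.25/7 = 0.179 over seven occasions. Its interaction noncentrality is 20 × 0.339/0.4 = 16.96, where 0.339 is the sum of squared deviations about the seven-occasion mean.

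| Test | Constant 0.5 SD | Fading |
|---|---|---|
| Six-visit average, covariate | 98% | 38% |
| One visit, covariate | 79% | 79% (month 1 or 3) |
| Group term, seven levels | 65% | 16% |
| Group-by-time term | 67% | 89% |

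**The case against.** The strongest reply is that Section 9 can be read narrowly. The trial is sized on one instrument, the ANOVA sentence speaks of differences between groups, and there is one null hypothesis. Read together, these suggest a single WOMAC group comparison, and its error rate is 5%. This stands as the likeliest intention. It does not settle the matter: sizing on an instrument does not make it the sole basis of the conclusion, the ANOVA sentence follows one about all measures, and a difference in course over time is also a difference between groups.

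Three stronger readings are tempting, and the documents do not support them.

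- *A reader might infer that the plan runs at 14% to 27% error.* That needs a rule that any positive result counts, which the plan does not state. The 27% also needs zero correlation between three knee questionnaires answered by the same patients, which is implausible.
- *A reader might infer that the silence on the pre-injection score inflates the error.* It does not once a use is fixed: as a level of time or as a covariate, the test holds 5%. Its role concerns power and what the group term measures.
- *A reader might infer that the choice of term flips the answer in nearly half of trials.* That rests on an assumed 0.5 SD, where both tests have power near two-thirds. At the difference implied by 25 per group, it is under one trial in ten with the planned recruitment.

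It is also fair to object that the six-visit average is not best in every case. Section 1 itself describes the benefit of HA injections as not lasting. Under the fading profile, the average with covariate still beats the seven-level group term, but falls far behind an early visit or the group-by-time term.

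**Conclusion.** The point holds as a gap in declaration. WOMAC and the group term are implied but not fixed, so the 5% rate for the Section 2 hypothesis is not guaranteed. The realistic exposure, should several results be allowed to decide, is a two-sided error of about 10% (WOMAC, either term) or about 8% to 11% (any instrument, one term, r from 0.9 to 0.7). About 27% is only an extreme bound.

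The effect on the answer ranges from small to large with the true difference, as step 5 shows. The loss of power from treating the pre-injection score as a time level is a second, separate finding.

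The first exposure needs no between-instrument correlation; the second depends on it. The disagreement and power figures rest on equal allocation, equal correlation between occasions, complete follow-up and the assumed effect profiles. The documents give none of these. Tests of subscales or of each visit would add to the error and were not counted.

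**What to change.** Before any comparison by arm, state in Section 9:

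(a) One named WOMAC score (for example the total) is the sole primary outcome.

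(b) The deciding test is one between-group contrast of follow-up WOMAC, either the average of the six follow-up visits or one pre-named visit. The pre-injection WOMAC is a covariate and not a level of time. The contrast is tested once at two-sided 0.05.

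(c) IKDC, KOOS, the group-by-time effect and other visits are secondary, reported with 95% confidence intervals and not used to claim efficacy. If claims on IKDC or KOOS are wanted, apply Holm across the three instruments for the same contrast.

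Both options in (b) hold 5%, but they answer different questions. The investigators should choose by how long they expect the benefit to last: the average suits a sustained difference, an early visit a fading one. Naming one instrument and one term is enough to secure the error rate; the covariate is there for power.

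The cost is wording only, with no new data or patients. A result confined to a secondary instrument, term or visit could no longer be called positive, and the average loses power if the effect fades. If Holm is used, its strictest step (0.05/3 = 0.0167) leaves 88% power with 40 per group and 65% with 25 for a 0.81 SD difference, by an unadjusted two-sample t-test.
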